3.3 Study Endpoints

Pilot Study

- Comparison of taste tests before and during chemotherapy

RCT

Primary endpoint:

- Comparison of the perception of bitterness induced by 500 ppm caffeine from week 1 to week 3 between the study group (HED mouthwash) and the control group (water mouthwash).

Secondary endpoints:

- Comparison of the perception of bitterness triggered by 500 ppm caffeine from week 1 to week 12 between the two groups.
- Comparison of the threshold for bitterness perception from week 1 to week 3 between the two groups.
- Comparison of the threshold for bitter taste perception in week 3 between the two groups.
- Comparison of overall taste perception in week 3 between the two groups.
- Comparison of overall taste perception from week 1 to week 12 between the two groups.
- Comparison of food intake using a 24-hour recall from week 1 to week 12 within the two groups.
- Comparison of food intake using a 24-hour recall from week 1 to week 12 between the two groups.
- Comparison of improvements in body composition from week 1 to week 12 between the two groups.

- Comparison of weight gain from week 1 to week 12 between the two groups.
- Comparison of quality of life using the EORTC-QLQ-30 Ovar and OV-28 from week 1 to week 12 within the two groups.
- Comparison of the change in quality of life using the EORTC-QLQ-30 Ovar and OV-28 from week 1 to week 12 between the two groups.
- Comparison of “patient-related outcomes” using a diary from week 1 to week 12 within the two groups.

4. Experimental Protocol

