4.1. Study Design

Pilot Study

This part of the study will include 40 female patients undergoing chemotherapy. Taste tests will be conducted before the start of chemotherapy and during the third cycle of chemotherapy. At these time points, blood samples will also be collected to determine zinc levels and the concentration of the chemotherapeutic agent, and a baseline medical history and taste-specific medical history will be assessed via questionnaire. Food intake is assessed once a week using a 24-hour recall, and during the third cycle of chemotherapy, saliva samples are additionally collected to serially evaluate the concentration of the chemotherapeutic agent in saliva.

RCT

This study is a double-blind, randomized, placebo-controlled trial investigating the effect of rinsing the mouth with HED before each main meal on the perception of bitterness over a 12-week period following completion of chemotherapy. Due to their prior treatments, patients undergo a detailed examination, including physical examination and preanesthetic assessment. In addition, a taste perception test is performed as part of the screening process. Furthermore, adverse events are reported during each chemotherapy cycle. In addition, a taste perception test is conducted as part of the screening process to identify any pre-existing taste disorders. If a general taste disorder is ruled out and an isolated disturbed perception of bitterness is confirmed, the patient can be included in the study.

A total of 32 patients will be included in the study (study group: 16 patients, placebo group: 16 patients). Depending on randomization, patients receive either a mouthwash containing HED and water or a mouthwash containing food coloring and water. In weeks 1, 3, and 12, an evaluation of bitter perception triggered by 500 ppm caffeine, a determination of the bitter perception threshold, and food intake assessment via a 24-hour recall questionnaire are conducted. In addition, at the same time points, the patients' quality of life is assessed using the EORTC-QCQ-30 Ovar and the OV-28 questionnaire. In addition, the patients' body

composition and weight will be assessed in week 1 and week 12. Patient-reported outcomes will be recorded using diaries.

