The patient returns for screening one week after her last cycle of chemotherapy due to suspected bitter phantogeusia. The patient's bitter phantogeusia is determined by directly asking about bitter taste perception ("Did you notice an increased bitter taste during the course of chemotherapy?") and subsequently classifying the increased perception as "mild," "moderate," or "severe." If the patient rates her heightened perception of bitterness as "moderate" or "severe," meets all inclusion and exclusion criteria, and consents to the study by signing the patient information form, she is eligible for inclusion in the study. As part of the screening examination, the threshold for bitter perception and the bitter perception triggered by 500 ppm caffeine are recorded. Body composition is also measured using the BOD POD® and a weight check is performed. Quality of life is assessed using the EORTC-QLQ-30 Ovar and OV-28, and dietary intake is assessed using a 24-hour recall questionnaire (GloboDiet). In addition, perception of the other four basic tastes (sweet, sour, salty, umami) is determined using a sensory test. Furthermore, the patient is given a detailed explanation of the necessary follow-up visits required as part of the study and is handed a diary.

Visit 2

The patient returns for a follow-up visit three weeks after the end of her last course of chemotherapy. A test is conducted to assess bitterness perception of 500 ppm caffeine and to determine the bitterness perception threshold, as well as a sensory test to assess perception of the taste qualities sweet, sour, salty, and umami, a quality-of-life assessment using the EORTC-QLQ-30 Ovar and OV-28, and a dietary intake assessment using the 24-hour recall questionnaire (GloboDiet).

Visit 3

The patient returns 12 weeks after the end of her last chemotherapy session for a final examination. A test of bitterness perception using 500 ppm caffeine and determination of the bitterness perception threshold is performed, along with a sensory test to assess perception of the taste qualities sweet, sour, salty, and umami, a measurement of body composition using the BOD POD®, and a weight check. Quality of life is assessed using the EORTC-QLQ-30 Ovar and OV-28, and dietary intake is assessed using a 24-hour recall questionnaire (GloboDiet). The diary is discussed and collected.

RCT: Overview of Study Visits

	CRF	QoL (EORTC 30 and OV-28)	Medication dispense/return	Sensory test	BOP POD	Weight	Diary	24-hour recall

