1.1. The Risk-Benefit Ratio

The homoeriodictyol to be administered in this study was published on the FEMA-GRAS (“generally recognized as safe”) list 22 by the FEXPAN expert panel of the Flavor and Extracts Manufacturers Association (FEMA) in the United States and has thus been deemed generally safe. Substances published on the GRAS list do not require further approval from the Food and Drug Administration (FDA) to be authorized for the market. NaHED (FL. - Number 16.083) has also been included in the EU’s positive list of permitted flavourings (Implementing Regulation No. 872/2012, Official Journal of the European Union, L 267/1) and is provided for this study by Symrise AG, Holzminden, Germany, in the specification required for use as a flavouring.

There are no risks for study participants, and no further examinations or interviews are required. All participants who complete the study will receive compensation for their time and effort in the amount of 130.00 euros. A portion of the compensation will be paid to the participants per visit (visit 1: 50 euros, visit 2: 30 euros, visit 3: 50 euros). For participants in the HED group, a benefit in the form of a reduction in the perception of bitterness is expected. In addition, a partial reduction in the perception of bitterness may also occur in the control group due to the placebo effect. The collected data can be used to facilitate the planning of a further, larger validation study to precisely evaluate the efficacy of HED in chemotherapy-induced bitter phantogeusia.

2. Legal Aspects

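### The diary outcome is compared only within each arm, so it does not use the randomised control and could be misread as a mouthwash effect

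*Combined protocol and SAP*

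**What the plan says.** Section 3.3 lists twelve secondary endpoints for the RCT. Three are within-group comparisons. Two of these have a between-group partner in the same list:

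- Food intake: "Comparison of food intake using a 24-hour recall from week 1 to week 12 within the two groups" and, as its own item, "Comparison of food intake using a 24-hour recall from week 1 to week 12 between the two groups".
- Quality of life: "Comparison of quality of life using the EORTC-QLQ-30 Ovar and OV-28 from week 1 to week 12 within the two groups" and, as its own item, "Comparison of the change in quality of life using the EORTC-QLQ-30 Ovar and OV-28 from week 1 to week 12 between the two groups".
- Diary: one item only, comparing patient-related outcomes "using a diary from week 1 to week 12 within the two groups".

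Elsewhere the diary appears only as a means of collection. Section 4.1 says "Patient-reported outcomes will be recorded using diaries", section 4.4.4 says that the outcomes are evaluated through it, and section 4.1.6 uses it for side effects rated on a VAS. No diary item, score or summary measure is defined as an outcome. The Statistical Analysis section (B.3) gives general tests for metric and categorical variables and does not mention the diary.

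**The concern.** The list uses within and between for two different comparisons, so the missing diary partner cannot be read as loose wording for a comparison of the arms. Followed as written, the diary endpoint is a before-after comparison in each arm.

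The setting makes such a comparison hard to interpret. On baseline timing, section 4.1.1 says: "The patient returns for screening one week after her last cycle of chemotherapy due to suspected bitter phantogeusia". The following weeks are a period in which recovery is plausible with or without HED. Section 2.1 suggests that HED might speed up taste-cell regeneration, which presupposes that some regeneration occurs anyway. Section C.1.1 allows for improvement on placebo: "a partial reduction in the perception of bitterness may also occur in the control group due to the placebo effect".

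A before-after change in the HED arm contains all of these. Setting a significant result in one arm beside a non-significant result in the other does not test the difference between them. The trial is randomised, double-blind and placebo-controlled so that shared change cancels out, and this endpoint makes no use of that.

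**Working it through.** The plan gives no effect size, SD or power for the diary, so there is no figure to reproduce. Its sample-size calculation concerns the primary endpoint, and only the group size and dropout rate are taken from it.

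**Inputs from the documents (section B.1).** 16 patients per arm; 20% dropout, so 16 × 0.8 = 12.8, about 13 completers per arm; significance level 1%, stated for the primary endpoint. The 5% level is added here as the conventional alternative.

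**Assumptions.** HED has no effect on the diary score. Both arms improve by the same amount, δ, in units of the SD of the change score. The main case is δ = 0.5, with a range of 0.3 to 0.8. Each arm is tested with a two-sided paired t-test, and the arms are independent.

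**Formulas.**
- Probability that one arm's test shows a significant improvement: P = Pr(T > t_crit), where T is noncentral t with n − 1 degrees of freedom and noncentrality δ√n.
- Probability that HED is significant and placebo is not: P × (1 − P).
- Between-group test of the change: the true difference is zero, so the rejection rate is the nominal level.

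**Main case, δ = 0.5.**

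| n per arm | δ√n | Level | t_crit | P (HED arm significant) | P × (1 − P) | Between-group test |
|---|---|---|---|---|---|---|
| 13 | 1.803 | 5% | 2.179 | 0.38 | 0.38 × 0.62 = 0.24 | 0.05 |
| 16 | 2.000 | 5% | 2.131 | 0.46 | 0.46 × 0.54 = 0.25 | 0.05 |
| 13 | 1.803 | 1% | 3.055 | 0.16 | 0.16 × 0.84 = 0.13 | 0.01 |
| 16 | 2.000 | 1% | 2.947 | 0.21 | 0.21 × 0.79 = 0.17 | 0.01 |

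**Range of P for δ = 0.3 to 0.8.** With 13 per arm: 17% to 75% at the 5% level, 5% to 47% at the 1% level. With 16 per arm: 20% to 85% and 7% to 61%.

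The exact values depend on δ, but the direction does not: any shared improvement raises the within-arm rate above the nominal level and leaves the between-group rate where it is.

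**The case against.** The strongest reply is that nothing in the plan says a within-arm diary change will count as evidence for HED. Section B.3 defines efficacy as a reduction in bitterness in the treatment group relative to placebo, and a diary change in one arm cannot meet that. This stands. A reader might infer that the plan will claim a mouthwash effect from the diary; the documents support only that the result could be misread that way.

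It follows that the percentages above are not false-positive rates of the test. If both arms really improve, rejecting no change is correct. The figures are the power to detect a shared change, and become false claims only if that change is attributed to HED.

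The plan also names no test for the diary. The t-test and Mann-Whitney U test in B.3 could be applied between the arms, but the plan does not say that they will be, and the listed comparison is within-group. The paired test used above is therefore an assumption.

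Some supporting evidence is indirect. The placebo sentence in C.1.1 concerns bitterness, not diary outcomes. Regression to the mean is a weak argument, because patients are selected by a retrospective question about taste during chemotherapy and not by a diary score. Recovery and placebo response are enough without it.

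Finally, one might want the tests dropped from the within-group food-intake and quality-of-life comparisons as well. Both already have between-group endpoints, so that would be a reporting preference and is not part of this point.

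**Conclusion.** The point holds in a limited form. The diary endpoint has no between-group comparison anywhere in the plan, and as listed it cannot separate an HED effect from recovery or placebo response. With an assumed shared improvement of 0.5 SD and no HED effect, the HED arm's own test would be significant in about 38% of trials at the 5% level with 13 completers per arm (46% with 16). At the 1% level the figures are about 16% and 21%. HED significant with placebo not would occur in about 24–25% of trials at the 5% level. These sizes rest on an assumed drift and an assumed paired test, because the documents give neither a diary SD nor a recovery rate. The structural gap does not depend on them. One of twelve secondary endpoints is affected, and the primary comparison is not.

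**What to change.** In section 3.3, make the diary endpoint a between-group comparison of one named diary score, either at week 12 or as the change to week 12. Keep the within-group diary change as a descriptive summary. State the test in section B.3.

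Take care with the baseline. The diary and the study medication are both handed out at Visit 1 (section 4.1.1 and its visit table), so first-week entries may be made on treatment. Adjusting for such a value, or measuring change from it, could remove part of any HED effect. Use a baseline only if the diary item is recorded before the first rinse; otherwise compare the week 12 values.

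The cost is small but goes beyond rewording: a diary score must be chosen and defined before the data are unblinded, and a pre-rinse entry added if a baseline is wanted. Diaries are already collected in both arms, so no extra patients or visits are needed.

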4.1. Study Design

Pilot Study

This part of the study will include 40 female patients undergoing chemotherapy. Taste tests will be conducted before the start of chemotherapy and during the third cycle of chemotherapy. At these time points, blood samples will also be collected to determine zinc levels and the concentration of the chemotherapeutic agent, and a baseline medical history and taste-specific medical history will be assessed via questionnaire. Food intake is assessed once a week using a 24-hour recall, and during the third cycle of chemotherapy, saliva samples are additionally collected to serially evaluate the concentration of the chemotherapeutic agent in saliva.

RCT

This study is a double-blind, randomized, placebo-controlled trial investigating the effect of rinsing the mouth with HED before each main meal on the perception of bitterness over a 12-week period following completion of chemotherapy. Due to their prior treatments, patients undergo a detailed examination, including physical examination and preanesthetic assessment. In addition, a taste perception test is performed as part of the screening process. Furthermore, adverse events are reported during each chemotherapy cycle. In addition, a taste perception test is conducted as part of the screening process to identify any pre-existing taste disorders. If a general taste disorder is ruled out and an isolated disturbed perception of bitterness is confirmed, the patient can be included in the study.

A total of 32 patients will be included in the study (study group: 16 patients, placebo group: 16 patients). Depending on randomization, patients receive either a mouthwash containing HED and water or a mouthwash containing food coloring and water. In weeks 1, 3, and 12, an evaluation of bitter perception triggered by 500 ppm caffeine, a determination of the bitter perception threshold, and food intake assessment via a 24-hour recall questionnaire are conducted. In addition, at the same time points, the patients' quality of life is assessed using the EORTC-QCQ-30 Ovar and the OV-28 questionnaire. In addition, the patients' body

composition and weight will be assessed in week 1 and week 12. Patient-reported outcomes will be recorded using diaries.

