4.1.2. Withdrawal from the study

Patients may withdraw from the study at any time without providing a reason. Withdrawal is defined as premature termination of the study prior to attending Visit 3. Every withdrawal is documented. Documentation up to the point of withdrawal must be complete. Patients who withdraw from the study will not be replaced. Patients who withdraw from the study will be included in the statistical analysis (intention-to-treat analysis). Patients who withdraw from the study must return all remaining study medication and will continue regular follow-up after gynaecologic cancer treatment at the Medical University of Vienna.

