4.1.3. Study Exclusion

Study exclusion refers to the exclusion of the patient from the study by the investigator (Associate [name] [name]). This occurs in the following cases:

- Occurrence of severe adverse events that seriously endanger the patient's health or life
- Other medical indications
- Demonstrable non-compliance by the patient
- Violation of the study protocol that, in the opinion of the investigator or the sponsor, is incompatible with the continuation of the study.

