4.1.6. Monitoring of side effects and adverse events

Side effects are documented in the patient's diary, and the patient uses a visual analog scale (VAS) to rate the severity of each side effect. Other adverse events and the use of other medications are also recorded in the patient's diary.

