4.2. Patients

Pilot Study

Inclusion Criteria

- 1) Patients (>18 years) with histologically confirmed gynaecological malignancy
- 2) Planned chemotherapy
- 3) Written informed consent
- 4) Expected patient compliance

Exclusion criteria:

- 1) Vomiting (CTCAE 4.03) > Grade 2 (3–5 episodes within 24 hours)
- 2) Nasogastric tube or PEG tube
- 3) Previous platinum-based chemotherapy
- 4) Conditions that impair taste perception (e.g., infections in the oral cavity)

Number of study participants:

A total of 40 patients will be enrolled in the study.

RCT

Inclusion criteria:

- 1) Patients (>18 years) with histologically confirmed ovarian cancer/tubal cancer/peritoneal cancer
- 2) Age 18–70 years
- 3) Non-smoker for at least 12 months
- 4) Completed chemotherapy with platinum and taxane
- 5) Written informed consent
- 6) Phantogeusia confirmed through patient interview
- 7) Expected patient compliance

Exclusion criteria:

- 1) Planned or ongoing treatment with a PARP inhibitor
- 2) Known intolerance to HED
- 3) Nausea and vomiting (CTCAE 4.03) > Grade 2 (3–5 episodes within 24 hours)
- 4) Nasogastric tube or PEG tube
- 5) Progressive tumour disease during adjuvant chemotherapy
- 6) Conditions that interfere with taste perception (e.g., infections in the oral cavity)
- 7) General taste disturbance verified by baseline tests

Number of study patients:

A total of 32 patients will be enrolled in the study (active treatment group: 16 patients, placebo group: 16 patients).

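### Adverse-event reporting in the RCT is tied to chemotherapy cycles that end before enrolment, and no assessed, by-arm safety record is planned for the mouthwash period

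*Combined protocol and SAP*

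**What the plan says.** - Section 4.1 (Study Design, RCT): "Furthermore, adverse events are reported during each chemotherapy cycle". The same subsection places the intervention "over a 12-week period following completion of chemotherapy".
- Section 4.2 (RCT inclusion criteria): "Completed chemotherapy with platinum and taxane".
- Section 4.1.1 (RCT Visit 1): "The patient returns for screening one week after her last cycle of chemotherapy due to suspected bitter phantogeusia".
- Section 4.1.6: "Side effects are documented in the patient's diary", with the severity of each side effect rated by the patient on a VAS. Other adverse events and other medications also go into the diary, with no grade or score stated.
- Section 4.1.1 (RCT visits): the diary is handed out at Visit 1 and is not mentioned in the Visit 2 text. At Visit 3, "The diary is discussed and collected". The overview table, however, marks both Diary and CRF at all three visits. It has no adverse-event column.
- Section 4.3.4: a patient who stops the mouthwash because of side effects has to tell the study team at once.
- Section 4.1.3: the investigator excludes a patient in the case of "Occurrence of severe adverse events that seriously endanger the patient's health or life".
- Section 4.1.2: "Patients who withdraw from the study must return all remaining study medication". Documentation up to withdrawal is to be complete, but the diary is not named among the items returned.
- Section 3.3 lists no safety endpoint, and Statistical Section 3 names no adverse-event analysis.

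**The concern.** The one sentence under the RCT heading that speaks of reporting adverse events refers to a period that is over when the patient enters. What is left for the treatment period is what the patient writes down, plus what she reports if she stops. No section has anyone ask about events at a mouthwash visit, grade them, judge whether they are related, or compare them between arms.

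Two things are at stake. First, section 4.1.3 gives the investigator a decision that depends on knowing about severe events, but no section says how the investigator learns of one in a patient who goes on rinsing. Second, the ethical section (1.1) states that participants face no risks and that the data should help plan a larger study. Without assessed events by arm, this trial can neither support that statement nor tell the next study how HED compares with placebo on tolerability.

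**Working it through.** The plan states no figure on this point, so there is none to reproduce. The check sets the sections side by side and does the date arithmetic.

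**1. Does any chemotherapy cycle fall inside the RCT?** Entry requires completed chemotherapy (4.2). Visit 1 is one week after the last cycle (4.1.1). Randomisation follows consent and the taste test (4.3.3), so the first rinse comes later still. Cycles during mouthwash use: 0.

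**2. What covers the mouthwash period?**

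| Source | Who starts it | What it gives | Whom it covers |
|---|---|---|---|
| Cycle-based reporting (4.1) | not stated | not stated | nobody on mouthwash |
| Diary (4.1.6) | patient | side effects with VAS; other events with no grade stated | all patients |
| Report on stopping (4.3.4) | patient | immediate notice | those who stop for side effects |
| CRF (overview table, 4.1.1) | marked at every visit | content not in the documents | all who attend |

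**3. When do staff see the diary?** By the visit text, at Visit 3. By the table, the diary is marked at Visit 2 as well, without saying what is done with it. The two need to be reconciled.

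**4. How long is the stretch without a planned contact?** The visit text counts from the end of chemotherapy (Visits 1, 2 and 3 at weeks 1, 3 and 12); the table counts from Visit 1.

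| | Visit text | Overview table |
|---|---|---|
| Visit 2, weeks after Visit 1 | 3 − 1 = 2 | 2 |
| Visit 3, weeks after Visit 1 | 12 − 1 = 11 | 12 |
| Visit 2 to Visit 3 | 11 − 2 = 9 weeks | 12 − 2 = 10 weeks |
| Share of Visit 1 to Visit 3 | 9/11 = 82% | 10/12 = 83% |
| Rinses, Visit 1 to Visit 3 (3 per day, 4.3.4) | 11 × 7 × 3 = 231 | 12 × 7 × 3 = 252 |

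The ± 3-day window (4.1.4) shifts the gap by at most 6 days. The weekly telephone recalls belong to the pilot study; in the RCT the 24-hour recall is marked at the three visits only.

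**5. Follow three patients through the plan.**
- One has a side effect and stops because of it: section 4.3.4 brings it to the study team at once.
- One has an event in week 1 and keeps rinsing: she attends Visit 2, but no text tells anyone to ask, and whether the diary is looked at depends on whether text or table is followed.
- One has an event in week 5 and keeps rinsing: she writes it down, and the next planned contact is Visit 3, 11 − 5 = 6 weeks later by the visit text or 12 − 5 = 7 by the table.

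In the last two cases, nothing planned before Visit 3 clearly informs the decision in section 4.1.3.

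**6. What reaches the analysis?** With no safety endpoint and no adverse-event analysis, no by-arm tabulation is planned even of what the diaries contain.

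**The case against.** The best defence is that the sentence in section 4.1 is not the RCT's safety rule at all. It stands within the screening description, next to the examination made because of prior treatment, and may simply record toxicity from chemotherapy. Statistical Section 3 uses such history (polyneuropathy during chemotherapy) as a predictor. The monitoring rule would then be section 4.1.6. This reading is plausible, but the gap remains: section 4.1.6 offers only the diary.

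Second, the visit text is not exhaustive. It also leaves out the CRF and the dispensing of medication, which the table marks at every visit, so silence about the diary at Visit 2 proves little. That stands, and it is why the point is a conflict to reconcile and not proof that the diary goes unread. The CRF may also contain an adverse-event page; its pages are not in the documents.

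Third, the product is a flavouring on the FEMA-GRAS and EU lists (ethical section 1.1), no tolerability endpoint is planned, and the primary endpoint, randomisation and efficacy analysis are untouched. This limits how serious the point is, but does not remove it.

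A reader might infer more than the documents support:
- *That staff do not see a patient with an event before week 12.* Every patient attends Visit 2, and section 4.1.2 suggests that routine oncology follow-up runs at the same institution.
- *That events in patients who stop early are the most likely to be missed.* Those who stop for side effects are the one group with an explicit immediate route (4.3.4), and documentation up to withdrawal must be complete (4.1.2).
- *That the exclusion rule could never be applied in time.* An endangering event may well lead to stopping, and so to a report.
- *That the cycle-based sentence is the only reporting by study staff.* It does not say who reports.

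**Conclusion.** The point holds as a gap that should be fixed; it does not threaten the primary result. The adverse-event sentence under the RCT heading covers no mouthwash time. On-treatment capture is a patient diary plus a report from those who stop for side effects. No section describes investigator assessment of events or an analysis by arm, and the exclusion rule in section 4.1.3 has no planned input from patients who keep rinsing.

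Its size: no planned contact for 9 to 10 weeks, about 82% to 83% of the interval from Visit 1 to Visit 3, over a course of roughly 231 to 252 rinses. The 20% dropout allowance (0.20 × 32 = 6.4, about 6 patients) is the order of magnitude of those for whom diary return is not spelled out; this does not mean that their diaries would be lost.

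This rests on two assumptions: that the visit text and overview table together give the full RCT contact schedule, and that no CRF page or separate procedure outside these documents already provides for adverse-event recording. If such a page exists, the remedy shrinks to describing it in the protocol and aligning the sections.

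**What to change.** Reconcile sections 4.1, 4.1.1 (visit text and overview table), 4.1.2, 4.1.3, 4.1.6 and 4.3.4. In particular:

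- In 4.1 (RCT), state that the investigator asks about adverse events and enters them in the CRF at Visit 2, Visit 3 and any early stop, covering the first rinse to the last visit. Record the CTCAE 4.03 grade (the version already used for eligibility), onset, outcome and relatedness. Keep the VAS as the patient's own rating.
- If the chemotherapy-cycle sentence is meant as pre-enrolment history, label it so.
- Align the Visit 2 text with the table, so that the diary is reviewed at Visit 2.
- In 4.1.2, name the diary among the items returned at withdrawal.
- In Statistical Section 3, add a tabulation of adverse events by arm in every patient with at least one rinse, the set already defined there as intention-to-treat.

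None of this alters the dose or the criteria for stopping or exclusion; it concerns what is recorded, when, and how it is reported. The cost is protocol wording, one CRF page and a few minutes at visits that already exist. It is best done before enrolment, because events not asked about at the time cannot be reliably recovered later.
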